1.5. Data analysis: In the evaluation of the data of the study, the number,%, mean and standard deviation will be given in descriptive statistics. Compliance of numerical data to normal distribution will be evaluated with Kolmogorow-Smirnow test. The homogeneity of the descriptive characteristics of the experimental and control groups will be evaluated with the Chi-square test for categorical variables, and parametric or nonparametric tests according to the normal distribution in numerical variables. In comparison of the scale scores (dependent variable results) of the two groups, dependent groups t test or Mann Whitney U test will be used according to the normal distribution feature. The scale scores of the groups before and after the intervention will be compared with the dependent sample t test or the wilcoxon test. Significance level will be accepted as $p < .05$.

References

1. WHO. Global status report on noncommunicable diseases 2014: attaining the nine global noncommunicable diseases targets; a shared responsibility. Global status report on noncommunicable diseases 2014: attaining the nine global noncommunicable diseases targets; a shared responsibility 2014.
3. Wise PH. The future pediatrician: the challenge of chronic illness. *The Journal of pediatrics*. 2007;151(5):S6-S10.
4. Theofanidis D. Chronic Illness In Childhood: Psychosocial Adaptation And Nursing Support For The Child And Family. *Health Science Journal*. 2007(2).

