Statistical analyzes were performed using a package program called SPSS (IBM SPSS Statistics 24). Frequency tables and descriptive statistics were used in the interpretation of the findings. In the analysis of all tests, p value <0.05 was considered statistically significant. The homogeneity of variances was evaluated by the "Levene test" and the conformity of the study data to normal distribution was evaluated by the "Shapiro-Wilk" test. According to this; "frequency distributions (number and percentage)" are given for independent variables.

"Independent Sample-t" test (t-table value) for comparing two independent groups for normally distributed data; "Paired Sample" test (t-table value) statistics were used in the comparison of two dependent groups. "Mann-Whitney U" test (Z-table value) in comparison of two independent groups for data that do not show normal distribution; "Wilcoxon" test (Z-table value) statistics were used to compare two dependent groups.

"Pearson correlation" analysis was used to examine the relationship between the mean scale of the two groups. Correlation coefficient; It has been accepted that there is a high relation between 0.70-1.00, a medium relation between 0.30-0.70, and a low level between 0.00-0.30

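### The protocol and SAP choose the between-arm test by different normality pre-tests and name different t tests, so the analysis is not fixed; verdicts would rarely change

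*Combined protocol and SAP*

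**What the plan says.** **Protocol, section 1.5 (Data analysis).** The pre-test is stated as "Compliance of numerical data to normal distribution will be evaluated with Kolmogorow-Smirnow test". For the scale scores of the two groups, "dependent groups t test or Mann Whitney U test will be used according to the normal distribution feature". Before-after comparisons within each group use a dependent-sample t test or Wilcoxon.

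**SAP (the closing Statistical Analysis section).** Levene's test is used for variances, and "the conformity of the study data to normal distribution was evaluated by the 'Shapiro-Wilk' test". The t branch is "Independent Sample-t' test (t-table value) for comparing two independent groups for normally distributed data". The other branch is the Mann-Whitney U "test (Z-table value) in comparison of two independent groups for data that do not show normal distribution".

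Neither text says:
- which variant of Kolmogorov-Smirnov is meant, or at what threshold a pre-test fails;
- whether baseline, post-test or change scores are pre-tested;
- whether the arms are pre-tested separately, and what follows if only one fails;
- which text prevails, or why the pre-test changed.

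No primary outcome is named. Quality of life is the only scale used to size the trial.

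**The concern.** The comparison of the two randomised arms is the one that carries the causal claim. Under either text its form depends on a test run on the trial's own data: a t test compares means, Mann-Whitney compares ranks. At 18 per arm the two pre-tests differ in sensitivity, so the same data could be sent down different branches depending on which text the analyst follows.

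The conflict over the t test is separate. A dependent t test needs pairs, and adolescents allocated by lot to two arms have none. Followed literally, the protocol would have the analyst invent a pairing.

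At stake is whether a reader can tell beforehand which test and which estimate answer the trial's question, and whether the analysis makes good use of 36 participants.

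**Working it through.** **Inputs from the documents.** Mean 69.1 and SD 17.1, target 82.8 (Sample Number Calculation); 18 per arm; significance at 0.05, taken as two-sided because sidedness is not stated.

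**Assumptions.** The documents give no post-test SD and no score shape. SD 17.1 is used in both arms before any clipping, and several shapes are tried.

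**The plan's own figure.** The difference is 82.8 − 69.1 = 13.7, and 13.7/17.1 = 0.80. The stated minimum of 15 is reproduced by a paired t test: noncentrality 0.8 × √15 = 3.10 on 14 df gives power 0.821. For two independent arms of 18, noncentrality is 0.8 × √(18/2) = 2.40 on 34 df, and power is 0.645. That is the starting point for judging efficiency below.

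**Simulation rule.** Pre-test each arm at 0.05. Use the t test if both arms pass, otherwise Mann-Whitney. Compare the route under Shapiro-Wilk with the route under Kolmogorov-Smirnov, either Lilliefors-corrected (L) or uncorrected (U). There were 3,000 to 4,000 trials per scenario.

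With a 13.7-point effect:

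| Assumed scores | Different test, L | Different test, U | Verdict changes, L | Verdict changes, U |
|---|---|---|---|---|
| Normal | 10% | 10% | 1.0% | 1.1% |
| Normal, clipped at 100 | 23% | 33% | 1.8% | 2.1% |
| Mild left skew | 18% | 24% | 1.4% | 2.3% |
| Normal, clipped at 92 | 32% | 77% | 2.1% | 4.6% |
| Strong left skew (gamma) | 28% | 71% | 2.9% | 11.3% |
| Beta on 0-100, strong ceiling | 30% | 80% | 2.8% | 10% |

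The clip at 92 is included because the protocol's description of the quality of life scale gives 92 as the maximum, alongside a per-item average; the range is not settled there.

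With no effect (normal, clipped at 100, mild and strong skew), the verdict changes in 0.4-0.6% (L) and 0.4-2.1% (U) of trials. Repeat runs put the low end near 0.2%. Type I error of the two-stage rule was 0.046-0.059 throughout.

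**Why U stands apart.** Uncorrected Kolmogorov-Smirnov with estimated mean and SD hardly ever rejects. On the beta scores it flagged non-normality in 2% of trials, against 56% for Lilliefors and 82% for Shapiro-Wilk.

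**How extreme the beta case is.** With mean 0.828 and SD 0.171, k = 0.828 × 0.172/0.171² − 1 = 3.87, so the parameters are 0.828k = 3.20 and 0.172k = 0.67. A second parameter below 1 makes the density climb without limit at 100. About 30% of the experimental arm would score above 95.

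**The t-test conflict.** On normal scores, a dependent t test on arbitrary pairs of 18 has power 0.620 against 0.645 for the independent test. The verdict differs in 7.7% of trials with the 13.7-point effect and 2.3% without.

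**What a fixed, baseline-adjusted analysis gains.** Adjustment shrinks the SD to 17.1 × √(1 − r²), where r is the pre-post correlation (not given in the documents). For r = 0.3, 0.5 and 0.7 this is 16.3, 14.8 and 12.2, so 13.7 points becomes 0.84, 0.93 and 1.12 SD. Simulated power rises from about 65% to 68%, 76% and 89%.

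**The case against.** Several points on the other side carry weight.

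- **The rule is pre-stated.** Both branches are named in advance, and the two-stage rule keeps type I error near 5%. This stands. A reader might infer that the pre-test inflates false positives, but the simulations do not show it.
- **Choosing another test rarely changes the answer.** This also stands. A reader might infer from an 80% disagreement in test choice that the trial's conclusion is a toss-up between the two texts. That figure needs uncorrected Kolmogorov-Smirnov, a variant the protocol does not specify, together with very strong skew that the documents do not describe. Even then about one verdict in ten changes. If the experimental-arm SD in the beta case is 12 instead of 17.1, the changes fall to 3.0% (U) and 1.6% (L).
- **The SAP is in the past tense.** It reads as a later account of what was done, not as a second rule in force. A reader might infer two live, competing plans; the wording does not bear that out. What remains is a change of method that is neither explained nor reconciled.
- **The dependent-groups wording may be a slip.** Probably so, since the protocol uses the dependent test correctly for before-after comparisons in the next sentence. It still needs correcting.

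**Conclusion.** The point holds as an inconsistency that should be corrected, with a modest numerical consequence. The two texts gate the between-arm test on different pre-tests, disagree on the t test, and leave the analysis to be settled by the data.

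Verdicts would change in about 0.2-3% of trials in most scenarios, in 4.6% with uncorrected Kolmogorov-Smirnov and scores clipped at 92, and in about 10% (11.3% at most) only with the uncorrected test and strong skew. All of this rests on assumed score shapes and an assumed post-test SD. The test-name conflict, read literally, matters more than the Lilliefors-corrected mismatch: 7.7% on normal scores with the planned effect.

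The cost to the trial is an analysis that is not fixed in advance and that leaves the baseline scores out of the between-arm comparison. It is not a loss of error control.

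**What to change.** 1. Remove the normality gate from both texts.
2. Name one between-arm analysis identically in protocol section 1.5 and the SAP: for each scale, ANCOVA of the post-test score on arm and baseline score. Use ordinary standard errors. If a robust version is wanted, specify HC3 with a t reference. An unspecified robust choice is risky at 18 per arm: type I error was 6-7% for HC0 with a normal reference, about 4% for HC3 with t, and about 5% for ordinary ANCOVA.
3. Correct the dependent-groups t test in section 1.5, which cannot apply to two independent arms.
4. Report Mann-Whitney as a fixed sensitivity analysis whatever the distribution, and say which score it is applied to.
5. State in the SAP that the method differs from the protocol's, and why.

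Cost: wording in two places and one residual degree of freedom (34 to 33). The baseline scores are already collected in both arms, so no new data or visits are needed.

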In a study conducted in our country, the mean quality of life score in children with celiac disease was found to be 69.1 ± 17.1 (49). According to this value, it was determined in the study that after the support program, it was aimed to increase the effect size of the quality of life scores by 0.8 (increase the quality of life from 69.1 ± 17.1 points to 82.8), and it was determined that at least 15 people should be included in the experimental group in calculating the sample number with 5% alpha error margin and 80% power. (G * Power 3.1.9.2). Considering the possible loss of patients, it was decided to enroll a total of 36 patients, 18 patients in the experimental group and 18 patients in the control group, with an excess of 10%.

Working groups will be assigned to the experimental and control groups by randomization by lot method.

1.4. Type of the study: The research was experimentally planned with pre-test, post-test control group.

1.5. Required manpower for research:

[name]. [name]: Coordinator of the research (creation of the method, follow-up of the application, evaluation of the findings, management of possible problems)

Lecturer . [name]: She will take part in the stages of obtaining institution and ethical approvals, implementation, data collection, data entry, interpretation and evaluation of study findings. In this process, information will be shared with the researcher.

Assoc. [name] [name]: She will contribute to the stages of obtaining patient records, sharing patient information and directing patients for application.

1.4. Research method and data collection tools:

Peer interactive group training will be applied for 3 months, one week apart, and will consist of 6 sessions in total. Support group meetings were planned to be held at the weekend in order to prevent adolescents' attendance at school. Adolescents will be contacted by phone before each session, and will be invited by informing about the date and time of the meeting. Each session will continue for 1.5 to 2 hours.

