Adolescents to be included in the control group will be administered an Introductory Information Form for Adolescents with a diagnosis of Celiac disease, the Quality of Life Scale for Children, the Peer Relations Scale, and the Coping Scale for Adolescents in the outpatient clinic in order to compare the effect of education in the hospital routine and peer interactive group support. After three months, the Adolescents in the control group will be re-administered the Quality of Life Scale for Children, the Peer Relationship Scale, and the Adolescent Coping Scale.

First Session; In this session, adolescents will be provided to share their knowledge of the disease. "What is celiac?", "What are the symptoms of celiac?" , "What does the celiac treatment include?" questions will be asked. By enabling adolescents to discuss among themselves, sharing of information, completing the missing information by the researcher and correcting the wrong information will be provided. In this session, Introductory Information Form, Children's Quality of Life Scale, Peer Relationship Scale, Adolescent Coping Scale will be applied to Adolescents with Celiac Diagnosis.

Second Session; In this session, to enable adolescents to share their difficulties with the disease, group members,

1- "How do you perceive living with celiac disease?"

2- "How is it an experience to live with celiac disease?", "How did celiac disease affect your life?"

3- "What are the difficulties you experience in daily life?"

4- "How do you deal with these problems in your daily life?", "What are the areas that you have difficulties in coping with the difficulties you experience?" questions will be asked.

Questions directed to the participants will be discussed among the group leader and participants.

The contents of the Third, Fourth, Fifth and Sixth sessions will be created regarding the problems identified in the first and second sessions. The determined problem areas will be discussed in each session. At the end of the sixth session, the Adolescents will be again applied to the Quality of Life Scale for Children, the Peer Relationship Scale, and the Adolescent Coping Scale.

After peer interactive group support, celiac patients will be given an educational booklet named "Living with Celiacs" to be created by the researcher.

In the content of the training booklet;

- What is celiac disease?
 - What are the symptoms of celiac disease?
- Celiac and life
- What is the treatment for celiac disease?

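### The between-arm tests make no stated use of the pre-test scores collected in both arms; adjusting for them would gain precision at little cost, provided the experimental arm's pre-test precedes the session-one content

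*Combined protocol and SAP*

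**What the plan says.** The protocol describes the design thus: "The research was experimentally planned with pre-test, post-test control group". Under Research method and data collection tools, the quality-of-life, peer-relations and coping scales are given to both arms twice. Controls complete them in the outpatient clinic and again later: "After three months, the Adolescents in the control group will be re-administered the Quality of Life Scale for Children". The experimental arm completes them in the first session and at the end of the sixth.

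For the comparison of arms, the protocol's Data analysis section (1.5) has "In comparison of the scale scores (dependent variable results) of the two groups, dependent groups t test or Mann Whitney U test", chosen by normality. The pre-test appears only in a second sentence: "The scale scores of the groups before and after the intervention will be compared with the dependent sample t test or the wilcoxon test". The SAP's Statistical Analysis section keeps this structure. It names the independent-samples test, a "test (t-table value) for comparing two independent groups for normally distributed data", with Mann-Whitney as the alternative, and paired or Wilcoxon tests within arms. Neither section names a baseline covariate, a change-score comparison or any other adjustment, and neither says which time point the between-arm test uses.

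For the experimental arm's first session, the protocol lists "completing the missing information by the researcher and correcting the wrong information will be provided" among the activities and then says of the forms: "Peer Relationship Scale, Adolescent Coping Scale will be applied to Adolescents with Celiac Diagnosis". It does not say which comes first.

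**The concern.** A randomised design with a pre-test in both arms offers a covariate that is already paid for. The plan leaves it out of the only comparison that estimates the effect of peer support against control. The within-arm tests do not fill the gap, because a before-after change in one arm is not a comparison with the other.

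Precision is scarce here. The SAP says that all 36 patients aged 13-18 followed at the centre were included, so the arms cannot be enlarged there. The sample size also falls short for a two-arm comparison, as shown below. Adjustment is therefore one of the few ways left to narrow the confidence interval.

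The pre-test is a safe covariate only if the intervention has not touched it. If the forms followed the session-one discussion, the experimental arm's pre-test may already carry part of the effect, and adjusting for it would bias the estimate.

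**Working it through.** **Inputs from the documents.** Effect size 0.8 (69.1 to 82.8 points with SD 17.1: 13.7/17.1 = 0.801), alpha 5%, power 80%, 18 per arm, 10% allowance for loss (18 × 0.9 = 16.2, taken as 16 completers).

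**Assumptions.** Two-sided testing (not stated); r from 0.3 to 0.7 (not given for quality of life or friendship quality); the 0.8 is a difference between arms, so controls do not change; normal scores; independent participants.

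**The plan's own figure.** The protocol says "at least 15 people should be included in the experimental group". A paired t test with effect size 0.8 has power 0.790 at n = 14 and 0.821 at n = 15, so the stated 15 is reproduced as a one-group before-after test. A two-sample t test has power of about 79% at 25 per arm and 81% at 26, so the between-arm comparison needs 26 per arm.

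**Unadjusted comparison.** Noncentral t with 2n − 2 degrees of freedom and noncentrality 0.8 × √(n/2). Power is 64.5% at n = 18 and 59.1% at n = 16.

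**ANCOVA.** Noncentral t with 2n − 3 degrees of freedom and noncentrality 0.8/√(1 − r²) × √(n/2)/√(1 + F/(2n − 2)), averaged over F with 1 and 2n − 2 degrees of freedom to allow for chance baseline imbalance. The variance relative to the unadjusted test is (1 − r²) × (1 + 1/(2n − 4)). At n = 18 and r = 0.5 this is 0.75 × 1.031 = 0.773, and the equivalent unadjusted size is 18/0.773 = 23.3 per arm. The half-width of the 95% CI is t(0.975, 2n − 3) × 17.1 × √(2/n × ratio).

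| | Unadjusted | r = 0.3 | r = 0.5 | r = 0.6 | r = 0.7 |
|---|---|---|---|---|---|
| Power, 18 per arm (%) | 64.5 | 67.2 | 75.5 | 81.8 | 89.5 |
| Power, 16 per arm (%) | 59.1 | 61.6 | 70.0 | 76.7 | 85.3 |
| Variance ratio, 18 per arm | 1 | 0.938 | 0.773 | 0.660 | 0.526 |
| Equivalent unadjusted n per arm | 18 | 19 | 23 | 27 | 34 |
| 95% CI half-width, points, 18 per arm | 11.6 | 11.2 | 10.2 | 9.4 | 8.4 |

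ANCOVA reaches 80% power at r of about 0.57 (18 per arm) or 0.64 (16 per arm). It breaks even with the unadjusted test at about 0.18 or 0.19. At r = 0 and 18 per arm, power falls from 64.5 to 63.1%.

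**Coping.** The protocol's KIDCOPE section gives three-week test-retest values of 0.66, 0.61 and 0.76. The ratios at 18 per arm are 0.582, 0.648 and 0.436, variance reductions of about 42, 35 and 56%. The trial interval is three months, so these are optimistic.

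**If session one shifts the experimental pre-test.** A shift of δ SD biases the ANCOVA estimate by −rδ. With δ = 0.2 (assumed) and r = 0.5, the estimate is 0.80 − 0.5 × 0.2 = 0.70. Simulation at 18 per arm with 40,000 trials per setting, and the break-even shift solved numerically:

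| δ = 0.2 SD | r = 0.3 | r = 0.5 | r = 0.6 | r = 0.7 |
|---|---|---|---|---|
| Mean estimate (true value 0.80) | 0.74 | 0.70 | 0.68 | 0.66 |
| Power (%) | 60 | 64 | 68 | 75 |
| Rejection with no true effect (%) | 5 | 6 | 7 | 9 |
| δ at which the power gain is gone (SD) | 0.08 | 0.19 | 0.24 | 0.30 |
| Same, in points (× 17.1) | 1.4 | 3.2 | 4.1 | 5.2 |

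A shift in the other direction inflates the estimate: δ = −0.2 gives about 0.86 to 0.94. The unadjusted post-test comparison is not affected by δ.

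**The case against.** The strongest reply is that nothing in the plan is invalid and that the proposed remedy may collapse into the plan as written. The order of forms and discussion is not established, and the SAP is in the past tense, so ANCOVA might end up as a post hoc sensitivity analysis. That is fair, and it limits what can now be recovered. It does not remove the case for stating the order and reporting the adjusted result.

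The size of the gain is also unknown for two of the three scales. At r = 0.3 it is under 3 points of power. This stands, and it is why a range is shown.

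The scale's stated maximum of 92 lies close to the target of 82.8: (92 − 82.8)/17.1 = 0.54 SD. Capping simulated scores at 92 lowers ANCOVA power at 18 per arm to about 72% (r = 0.5) and 78% (r = 0.6), so 80% is no longer reached at 0.6. The unadjusted test falls too, to about 62%, so the relative gain remains. Group delivery could make outcomes within the experimental arm correlated, and no figure here allows for that.

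The quality-of-life scale asks about the past month, which makes a large same-day shift less likely for that scale. This softens the worry about session one but does not settle the order. The excess false-positive rate arises only when the pre-test is contaminated, and in that case ANCOVA should not be the main analysis.

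**Conclusion.** The point holds as a recommended improvement, not as an error of validity. The pre-test is available in both arms and has no stated role in the between-arm test. Using it at 18 per arm would be worth about 1 extra patient per arm if r = 0.3, 5 if r = 0.5, 9 if r = 0.6 and 16 if r = 0.7, against a worst-case loss of about 1.4 points of power.

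Adjustment does not by itself repair the sample-size shortfall. Power returns to 80% only if r is at least about 0.57, or about 0.64 with 16 completers per arm. The omission is certain from the text. The size of the gain depends on the assumed r, on no change in controls, and above all on a pre-test taken before the session-one content.

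**What to change.** 1. State that the post-test score is the one compared between arms.
2. Name one main between-arm analysis per score: ANCOVA of the post-test on arm with the pre-test of the same score as covariate, reported as an adjusted mean difference with 95% CI. Use a rank or permutation version if residuals are clearly non-normal. For coping, the KIDCOPE section defines only subscale scores whereas the SAP lists total scores as the dependent variables; settle which is analysed before fitting the model.
3. State under Research method that the experimental arm completes the pre-test before any session-one content. If that was not so, or cannot be established, keep the unadjusted post-test comparison as the main analysis and give ANCOVA as a sensitivity analysis.
4. Label the within-arm tests as descriptive.
5. Correct the protocol's reference to a dependent-groups test between arms, a wording slip that the SAP already resolves.

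If the analyses have been run, report ANCOVA beside the planned test and label it post hoc.

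The cost is a few sentences in three sections and one SPSS model per score, with one degree of freedom each and no new data. It stays this low only if the condition in item 3 is met.
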